9.2 Disposition of Subjects

The number of subjects screened will be provided. The number and percentage (based on the number of subjects screened) of screen failures will also be provided, as well as the reasons

Confidentiality Statement

Data and information contained in this document are considered to constitute trade secrets and confidential commercial information, and the legal protections provided to such trade secrets and confidential information are hereby claimed under the provisions of applicable law. No part of this document may be publicly disclosed without the written consent of Philip Morris Products S.A

for screen failures. The number and percentage (based on the number of subjects screened) of enrolled but not randomized subjects will also be reported.

Randomized subject disposition will be summarized by absolute counts (n) and percentages (%) and split by randomization arm and overall. Percentages will be based on the number of subjects in each randomization arm or overall. The number of subjects who completed the study, the number of subjects who prematurely discontinued, and the primary reason for withdrawal will be reported.

Disposition data will be listed.

9.3 Demographic and Other Baseline Characteristics

Demographics and baseline characteristics will be summarized as follows:

- By randomized study arm for the FAS
- By randomized study arm for the PPS
- By randomized study arm or a group of enrolled but not randomized subjects when applicable for the SAF

Demographic variables will include sex, age (years), race, body weight (kg), height (m), body mass index (BMI, kg/m²). Body weight and BMI will be summarized at screening and admission. Baseline characteristics include TNP use history (average product use per day in the last four weeks, number of participants with continuous product use for the past 3 years, and other questions included in the Nicotine/Tobacco Product Use History questionnaire), spirometry measurements (FEV1, FEV1 % predicted, FVC, FVC % predicted, and FEV1/FVC), and FTND questionnaire score.

All demographic and baseline characteristics data will also be summarized using the stratification factors provided in section [9.1.1](#).

All demographic and baseline characteristics data will be listed.

9.4 Measurement of Product Compliance

The distribution and return of the THS devices will be documented in appropriate logs. Used THS sticks and CIG butts will be collected and documented for accountability. These data will be presented in listings.

Confidentiality Statement

Data and information contained in this document are considered to constitute trade secrets and confidential commercial information, and the legal protections provided to such trade secrets and confidential information are hereby claimed under the provisions of applicable law. No part of this document may be publicly disclosed without the written consent of Philip Morris Products S.A.

9.5 Extent of Exposure (Product Consumption)

All subjects in one of the THS variant arms (Blade device, or Induction Mono device, or Induction Mid device, respectively) and CIG arms will be permitted *ad libitum* use of the respective products.

This data will be summarised for the FAS, PPS, and SAF, as well as stratified using the factors described in section 9.1.1, as follows:

For the CIG group, the following parameters will be summarized:

1. Number of cigarette butts and percent change from baseline for Day 1, 2, 3, 4, 5,
2. Average number of cigarette butts per day (computed using the sum of all cigarette butts collected over Days 1-5 divided by the number of days spent by the subject in the exposure period) and percent change from baseline,
3. Total cigarette butts over 5 days.

For every THS arms (Blade device, or Induction Mono device, or Induction Mid device, respectively), the following parameters will be summarized:

1. Number of used THS sticks for Day 1, 2, 3, 4, 5,
2. Average number of used THS sticks per day (computed using the sum of all used sticks over Days 1-5 and divided by the number of days spent by the subject in the exposure period),
3. Total number of used sticks over 5 days.

All exposure data will also be listed.

9.6 Planned Statistical Analyses

9.6.1 Primary Objective: Primary Estimand Analysis

The primary objective of the study is to demonstrate the reduction of BoExp to selected HPHC in smokers switching from CIG to each of the THS arms (THS Blade device and THS Induction Mono device and THS Induction Mid device) compared to continuing CIG smoking for 5 days.

9.6.1.1 Primary Estimand

The primary estimand of the primary objective is defined by the following components:

1. Product Use Under Evaluation: This corresponds to the study arms (CIG, THS Blade device, THS Induction Mono device or THS Induction Mid device) randomly allocated to subjects and for which they have fulfilled key compliance criteria of the protocol

Confidentiality Statement

Data and information contained in this document are considered to constitute trade secrets and confidential commercial information, and the legal protections provided to such trade secrets and confidential information are hereby claimed under the provisions of applicable law. No part of this document may be publicly disclosed without the written consent of Philip Morris Products S.A

without major protocol deviation impacting the evaluability of the primary objective (as defined by the PPS).

2. **Target Population**: This is the population of adult smokers who satisfy all eligibility criteria (see section [4.5.1](#)).
3. **Variables of Interest**: 3-HPMA, 2-CyEMA, total NNAL, MHBMA (all expressed as concentration adjusted for creatinine in 24-hour urine), and COHb (expressed as % of saturation of hemoglobin).
4. **Intercurrent Events (ICEs)**:
 1. Non-adherences to the randomization study arm: these ICEs are out of scope of this primary estimand, and related subjects will be excluded from this analysis.
 2. Study discontinuation and death: data related to subjects who discontinued or died during the exposure period will be included only if they were adherent until the time of discontinuation/death.
 3. Subjects being tested SARS-CoV-2 positive during the study: these subjects will be included only until the time of the diagnosis. Data collected after or at the date of the SARS-CoV-2 positive test will be reported as missing.
 4. Changes in comorbidities: subjects with comorbidities or worsening of an existing comorbidity will be included as this change may be linked to the reduction or modification of their CIG consumption.
5. **Population-Level Summary Statistic**: geometric mean ratios between every THS arms (THS Blade device, THS Induction Mono device or THS Induction Mid device) and CIG of the BoExp under consideration at Day 5.

9.6.1.2 Main Analysis

The primary analysis will be conducted in the PPS and based on a mixed model for repeated measurements (MMRM). An unstructured matrix will be used to model the variance-covariance structure within subjects. If this model fails to converge, then the following variance-covariance matrix will be used (in order) until one converges: Heterogeneous Toeplitz, Heterogeneous First Order Autoregressive, Heterogeneous Compound Symmetry, Variance Components, Compound Symmetry, and finally no repeated statement.

The model for the endpoint expressed on the log-scale will adjust for the endpoint value at baseline (log-scale), the Day, the randomization study arm and its interaction with Day, and sex.

Confidentiality Statement

Data and information contained in this document are considered to constitute trade secrets and confidential commercial information, and the legal protections provided to such trade secrets and confidential information are hereby claimed under the provisions of applicable law. No part of this document may be publicly disclosed without the written consent of Philip Morris Products S.A

The model described above will be implemented in the SAS® language as:

```
PROC MIXED data=dataset method=reml nobound;
  class Arm Day Subject Sex;
  model Log(Endpoint) = Log(Baseline) Day Arm Arm*Day
    Sex / ddfm=kenwardroger solution;
  repeated Day / subject=Subject(Arm) type=un rcorr;
  lsmeans Arm*Day / pdiff cl;
  lsmeans 'Contrast every THS arms (THS Blade Device 1,
  THS Induction Device 1 or THS Induction Device 2) vs. CIG' exact
  syntax to be adjusted depending on the coding of class variables
  / cl upper alpha=0.025;
RUN;
```

LS-means per randomization study arm and day will be obtained (on the log-scale), as well as pairwise differences between arms per day, together with their 95%-confidence intervals and (unadjusted) p-values. Exponentiation of these quantities will lead to the geometric LS-means per randomization study arm and (geometric) ratios between arms with their associated 95%-confidence intervals.

The exponentiation of the ‘lsmeans’ statement above entitled ‘Contrast every THS arms (THS Blade device, THS Induction Mono device, or THS Induction Mid device) vs. CIG’ will allow contrasting all THS arms jointly against the CIG arm and will be used to assess the primary study hypothesis (see section 3.1).

For each individual BoExp in the Primary Analysis, the hypothesis will be evaluated using the 1-sided statistical test with a type I error level of 2.5% given by the ‘lsmeans’ statement ‘Contrast every THS arms (THS Blade Device 1, THS Induction Device 1 or THS Induction Device 2) vs. CIG’ of the model described in this section.

The study will be declared successful if all ratios of the geometric means between every THS arms (THS Blade device, THS Induction Mono device or THS Induction Mid Device) over CIG is statistically lower than 1 at Day 5 for all five Primary BoExp.

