6 SAMPLE SIZE JUSTIFICATION

In this study, 80 healthy smokers will be randomized in a 1:1:1:1 randomization ratio stratified by sex with an overall quota of 40% per sex to:

1. THS Blade device arm
2. THS Induction Mono device arm
3. THS Induction Mid device arm
4. CIG arm

Based on four previous similar studies conducted by PMP on the tobacco heating system ([ClinicalTrials.gov](#) identifiers are NCT01970995, NCT01989156, NCT01959932, and

Confidentiality Statement

Data and information contained in this document are considered to constitute trade secrets and confidential commercial information, and the legal protections provided to such trade secrets and confidential information are hereby claimed under the provisions of applicable law. No part of this document may be publicly disclosed without the written consent of Philip Morris Products S.A.

NCT01970982, respectively), [Table 7](#) contains estimates of geometric mean ratios (GMR) and associated coefficients of variations (GCV) for the (adjusted) contrast of a tobacco heating system against CIG. The effect of THS is expected to be similar on the selected BoExp. In addition, based on these studies, a conservative estimation of 15% of missing values may be expected for various reasons (e.g., withdrawals, mis-randomization, etc.).

Using the statistics displayed in [Table 7](#), the sample size planned for this study accounting for 15% of missing values (resulting in 20 subjects for each THS arms and 20 subjects in CIG arms, respectively), and a one-sided two-sample t-test (on the log-scale) with 2.5% type I error probability, the estimated power for each BoExp is displayed in [Table 7](#). By multiplying the power for each individual BoExp over the five to be tested in the primary hypothesis (per study), a global estimate of power for each THS arm is obtained. Assuming independence of the THS arms, the overall power of the study is equal or larger than $97\% = 99\%^3$ (to account for the 3 THS arms) for the primary objective.

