9.6.1.3 Supportive/Sensitivity Analyses

The model described in section 9.6.1.2 allows contrasting all randomization study arms at Days 1, 2, 3, 4, and 5. While only the contrast between the three THS arms jointly and CIG at Day 5 will be used for the primary objective assessment, the following pairwise comparisons

Confidentiality Statement

Data and information contained in this document are considered to constitute trade secrets and confidential commercial information, and the legal protections provided to such trade secrets and confidential information are hereby claimed under the provisions of applicable law. No part of this document may be publicly disclosed without the written consent of Philip Morris Products S.A

at Days 1, 2, 3, 4, and 5 will also be reported, together with their unadjusted p-values and 95% confidence interval:

1. THS arms jointly (THS Blade device, THS Induction Mono device or THS Induction Mid device) vs. CIG
2. THS Blade device vs. CIG
3. THS Induction Mono device vs. CIG
4. THS Induction Mid device vs. CIG

Contrasts THS Blade device vs. CIG and THS Induction Mono device vs. CIG and THS Induction Mid device vs. CIG will also be estimated one-sided with a type I error level of 2.5% through the additional ‘lsmestimate’ statements. These contrasts will be used to assess the key secondary objectives 1, 2 and 3 if the procedure of fixed sequence testing (see section 9.6.3.1) allows.

Descriptive statistics as mentioned in section 9.1.3 for the variables of interest and associated changes from baseline will be reported by randomization study arm for the PPS and by study day. Descriptive statistics stratified by the factor described in section 9.1.1 will also be computed.

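### The covariance fallback in effect stops at one variance pooled over Days 1–5; if variance differs by day, the Day 5 test would miss its 2.5% level in either direction (minor)

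*SAP*

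**What the plan says.** SAP 9.6.1.2 starts from the richest structure: "An unstructured matrix will be used to model the variance-covariance structure within subjects". It then states: "If this model fails to converge, then the following variance-covariance matrix will be used (in order) until one converges". The list is "Heterogeneous Toeplitz, Heterogeneous First Order Autoregressive, Heterogeneous Compound Symmetry, Variance Components, Compound Symmetry, and finally no repeated statement". The part at issue is its end: "Variance Components, Compound Symmetry, and finally no repeated statement". Protocol 12.5.1.4 has the same list in the same order. Non-convergence is the only trigger for moving down.

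The model for each log-scale biomarker adjusts for log baseline, "the Day, the randomization study arm and its interaction with Day, and sex". The SAS code puts Day on the REPEATED statement with no grouping option, uses Kenward-Roger degrees of freedom and asks for no robust standard error.

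Each primary biomarker is judged by a "1-sided statistical test with a type I error level of 2.5"%. SAP 9.6.1.3 adds that "only the contrast between the three THS arms jointly and CIG at Day 5 will be used for the primary objective assessment". The same model serves the seven key secondary biomarkers, arm by arm (SAP 9.6.3.1). The confirmatory tests use the PPS; the FAS repeat is exploratory (SAP 9.6.2.2 and 9.6.3.1). Neither document gives variances by day or within-subject correlations.

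**The concern.** A fallback list should run from complex to simple, and each step should be reachable. Here Variance Components, with one parameter, comes before Compound Symmetry, which has two and contains it. Because the one-parameter fit does not fail, the last two steps are dead and the effective floor is independent errors with a common variance.

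The confirmatory question concerns Day 5 alone. At that floor its standard error comes from the five-day average variance. If Day 5 is more variable than the average day, the test is too liberal; if less variable, too conservative. SAP 9.1.7 states that the one-sided 2.5% level is preserved, and that would then not be so for any biomarker analysed at this step.

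**Working it through.** **1. The plan's own figure.** The plan states power above 99% per biomarker, with "80 healthy smokers will be randomized in a 1:1:1:1 randomization ratio" and 15% loss (20 per arm, 17 evaluable). With SD = √ln(1+GCV²), difference |ln GMR| and a one-sided 2.5% two-sample t-test, the weakest primary row (3-HPMA, NCT01970982: GMR 52.86%, GCV 39.57%) gives SD = √ln(1+0.3957²) = 0.381 and a difference of 0.638. Power is 99.93% at 20 per arm and 99.71% at 17. The lowest study-wise product at 17 is 99.57%, and 0.9957³ = 98.7%, above the stated 97%. The stated power reproduces.

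**2. The order.** Covariance parameters for five days:

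- unstructured: 5×6/2 = 15
- Heterogeneous Toeplitz: 5+4 = 9
- Heterogeneous AR(1): 5+1 = 6
- Heterogeneous Compound Symmetry: 5+1 = 6
- Variance Components: 1
- Compound Symmetry: 2
- no REPEATED statement: 1

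The REML estimate for Variance Components is the residual sum of squares over its degrees of freedom. Nothing is iterated, so nothing fails to converge.

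**3. Effect of ignoring correlation alone.** With Arm*Day in the model, the Day 5 arm difference is a between-subject comparison, and its variance is essentially the Day 5 variance over n whatever the correlation. What changes is mainly the degrees of freedom. At 17 per arm there are 68×5 = 340 values less 4×5+2 = 22 mean parameters, so 318 df (critical t 1.967). A Day 5 ANCOVA has 68−6 = 62 df (critical t 1.999). Simulated level of the joint contrast with equal variances and correlation 0 / 0.5 / 0.8 / 0.9 (30,000 null trials each, Monte Carlo error about 0.09 points):

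- 20 per arm: 2.41 / 2.75 / 2.72 / 2.71%
- 17 per arm: 2.50 / 2.61 / 2.72 / 2.80%

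**4. Effect of unequal variance over days.** Let r = √(mean variance over Days 1–5 ÷ Day 5 variance). The model's standard error is about r times the true one, so the actual level is about 1−Φ(1.96 r). Simulations with 17 per arm and correlation 0.8 (patterns assumed):

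| Pattern | r | 1−Φ(1.96 r) | Variance Components | Compound Symmetry | Day 5 ANCOVA |
|---|---|---|---|---|---|
| Day 5 SD 1.25× other days | √(1.1125/1.5625) = 0.844 | 4.9% | 5.14% | 4.71% | 2.42% |
| Day 5 SD 1.5× other days | √(1.25/2.25) = 0.745 | 7.2% | 7.51% | 7.05% | 2.44% |
| SD rising 0.6 to 1.0 | √(0.66/1) = 0.812 | 5.6% | 5.75% | 5.35% | 2.48% |
| Day 5 SD 0.8× other days | √(0.928/0.64) = 1.204 | 0.9% | 1.13% | 0.96% | 2.51% |
| SD falling 1.0 to 0.6 | √(0.66/0.36) = 1.354 | 0.4% | 0.57% | 0.50% | 2.51% |

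The same check by Day 5/Day 1 variance ratio. The approximation takes variance changing in equal steps. The simulations use 17 per arm, AR(1) 0.7 and baseline slope 0.5; ranges cover repeated runs:

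| Ratio | r | 1−Φ(1.96 r) | Simulated, Variance Components |
|---|---|---|---|
| 2 | √(1.5/2) = 0.866 | 4.5% | 4.4–5.2% |
| 3 | √(2/3) = 0.816 | 5.5% | 5.6–5.9% |
| 5 | √(3/5) = 0.775 | 6.4% | 6.6–6.8% |
| 1/2 | √(0.75/0.5) = 1.225 | 0.8% | 0.9–1.1% |
| 1/3 | √(0.667/0.333) = 1.414 | 0.3% | 0.3% |
| 1/5 | √(0.6/0.2) = 1.732 | 0.03% | 0.07% |

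Across all these unequal-variance settings the Day 5 ANCOVA stays at 2.1–2.7%.

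**5. One route to a larger Day 5 variance.** The model has a single baseline slope and no baseline-by-day term. If correlation with the Day −1 value fades over the week, residual variance grows towards Day 5 even when raw variance is constant. With assumed serial correlation of 0.7–0.9, the level under Variance Components is about 3.7–5.6%.

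**The case against.** **The step may never be used.** Four structures must fail first, with five scheduled days and about 68 to 80 subjects. The documents give no basis for a probability, but it should be small. This stands, and it is the main reason for the low severity.

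**The primary conclusion would hardly move.** In the weakest primary row at 17 per arm, the pairwise standard error is 0.381×√(2/17) = 0.131, so the expected t is 0.638/0.131 = 4.9 against a critical value near 2. With the standard error overstated by 1.354 it is still 4.9/1.354 = 3.6. Every biomarker must also pass at each level, so one test on a fallback structure cannot produce success alone. This stands too.

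**Variance Components might be meant as one variance per day.** On a REPEATED statement with no grouping option, as in the SAP code, it is one common variance. If day-specific variances are intended, the SAP has to say so.

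**Stronger readings.** A reader might infer that the plan's Day 5 test is anti-conservative because it treats five daily values as independent and counts each subject five times. The documents do not support that: the excess from correlation alone is at most about 0.3 points, and with no variances by day the direction of the larger error is unknown. Nor does the sequence run down to dropping the REPEATED statement; it stops one model earlier in name, though at the same model in substance.

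**Conclusion.** The point holds as a minor defect in the specification. Two listed steps cannot be reached, and the effective floor assumes one variance over Days 1–5 while the confirmatory contrast is at Day 5. If that floor were used, the one-sided level would be about 2.5–2.8% with equal variances, about 4.5–7% with a Day 5 variance 2 to 5 times Day 1, and about 0.1–1% with one half to one fifth. The cause is the pooled variance, not the independence assumption, and Compound Symmetry shares it (4.7–7.1% and 0.5–1.0% in the first table's patterns).

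These figures rest on complete-data simulations, equal variance across arms, and assumed correlations and variance patterns. A reader might conclude that the trial's error control or its primary result is in doubt. That does not follow: the first-choice model and the three structures after it all allow a separate variance for each day, only the PPS tests are confirmatory, and the stated power above 99% reproduces.

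**What to change.** In SAP 9.6.1.2, end the list at Heterogeneous Compound Symmetry. Replace the last three steps with one sentence: if no structure up to that point converges, the confirmatory contrasts for that biomarker are tested by an ANCOVA of the log Day 5 value on log baseline, arm and sex, one-sided at 2.5%. Record the change in SAP section 7, since protocol 12.5.1.4 carries the same list.

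The cost is that sentence and the entry. The downside is that the ANCOVA does not use Days 1–4 for subjects missing Day 5. At the planned 15% loss that leaves 17 per arm, where the planning power is still above 99%.

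Two lighter edits would not be enough. Moving Compound Symmetry ahead of Variance Components keeps the equal-variance assumption, and deleting the final step removes something that is never reached. Empirical (sandwich) standard errors would address the cause, but only with a small-sample correction: uncorrected, they gave about 2.9–3.5% at 17 per arm, including 3.3% with equal variances.

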9.6.1.3 Supportive/Sensitivity Analyses

The model described in section 9.6.1.2 allows contrasting all randomization study arms at Days 1, 2, 3, 4, and 5. While only the contrast between the three THS arms jointly and CIG at Day 5 will be used for the primary objective assessment, the following pairwise comparisons

Confidentiality Statement

Data and information contained in this document are considered to constitute trade secrets and confidential commercial information, and the legal protections provided to such trade secrets and confidential information are hereby claimed under the provisions of applicable law. No part of this document may be publicly disclosed without the written consent of Philip Morris Products S.A

at Days 1, 2, 3, 4, and 5 will also be reported, together with their unadjusted p-values and 95% confidence interval:

1. THS arms jointly (THS Blade device, THS Induction Mono device or THS Induction Mid device) vs. CIG
2. THS Blade device vs. CIG
3. THS Induction Mono device vs. CIG
4. THS Induction Mid device vs. CIG

Contrasts THS Blade device vs. CIG and THS Induction Mono device vs. CIG and THS Induction Mid device vs. CIG will also be estimated one-sided with a type I error level of 2.5% through the additional ‘lsmestimate’ statements. These contrasts will be used to assess the key secondary objectives 1, 2 and 3 if the procedure of fixed sequence testing (see section 9.6.3.1) allows.

Descriptive statistics as mentioned in section 9.1.3 for the variables of interest and associated changes from baseline will be reported by randomization study arm for the PPS and by study day. Descriptive statistics stratified by the factor described in section 9.1.1 will also be computed.

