### 12.9.3 Study Significance Level

In this study, the overall familywise type I error will be preserved at the  $\alpha$ -level of 2.5% (1-sided tests will be conducted for the primary and key secondary study hypotheses). This will be done by using a fixed sequence of testing:

- primary objective, then if significant
- 1st key secondary objective, then if significant
- 2nd key secondary objective, then if significant
- 3rd key secondary objective

All objectives will be tested at the 2.5% type I error level until one of the objectives is rejected and no further testing will be performed (in this case, only subsequent exploratory testing will be conducted).

The primary study hypothesis (as assessed using the primary estimand defined in section 12.5.1) will be tested one-sided with a type I error  $\alpha$ -level of 2.5%. The associated 1-sided 97.5% confidence interval will be provided. This will be applied to all BoExp of Table 3 that are part of the primary study hypothesis (every BoExp for each THS arms need to pass for the objective to be considered demonstrated).

If the primary study hypothesis is demonstrated, the same  $\alpha$ -level of 2.5% will be used for the 1st key secondary hypothesis and the associated 1-sided 97.5% confidence interval will be provided. This will be applied to all BoExp of Table 4 that are part of the 1st key secondary study hypothesis (all need to pass for the THS Blade device arm versus CIG for the 1st key secondary objective to be successful).

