3.5 Study Hypotheses and Evaluation Criteria

3.5.1 Hypotheses

The primary study hypothesis is that there is a reduction of each and every of the BoExp to the selected HPHC that are examined for the primary objective, in subjects switching to one of the THS products (THS Blade device, THS Induction Mono and THS Induction Mid) compared to subjects continuing CIG at day 5.

Specifically, the primary hypothesis (H_1) is:

- The geometric mean ratio (THS Blade device/CIG) of 3-HPMA at Day 5 is less than 1 and
- The geometric mean ratio (THS Blade device/CIG) of 2-CyEMA at Day 5 is less than 1 and
- The geometric mean ratio (THS Blade device/CIG) of MHBMA at Day 5 is less than 1 and
- The geometric mean ratio (THS Blade device/CIG) of total NNAL at Day 5 is less than 1 and
- The geometric mean ratio (THS Blade device/CIG) of COHb at Day 5 is less than 1 and
- The geometric mean ratio (THS Induction Mono/CIG) of 3-HPMA at Day 5 is less than 1 and
- The geometric mean ratio (THS Induction Mono/CIG) of 2-CyEMA at Day 5 is less than 1 and
- The geometric mean ratio (THS Induction Mono/CIG) of MHBMA at Day 5 is less than 1 and
- The geometric mean ratio (THS Induction Mono/CIG) of total NNAL at Day 5 is less than 1 and
- The geometric mean ratio (THS Induction Mono/CIG) of COHb at Day 5 is less than 1 and
- The geometric mean ratio (THS Induction Mid/CIG) of 3-HPMA at Day 5 is less than 1 and
- The geometric mean ratio (THS Induction Mid/CIG) of 2-CyEMA at Day 5 is less than 1

Confidentiality Statement

Data and information contained in this document are considered to constitute trade secrets and confidential commercial information, and the legal protections provided to such trade secrets and confidential information are hereby claimed under the provisions of applicable law. No part of this document may be publicly disclosed without the written consent of Philip Morris Products S.A.

and

- The geometric mean ratio (THS Induction Mid/CIG) of MHBMA at Day 5 is less than 1
and
- The geometric mean ratio (THS Induction Mid/CIG) of total NNAL at Day 5 is less than 1
and
- The geometric mean ratio (THS Induction Mid/CIG) of COHb at Day 5 is less than 1

For the key secondary objective, the hypotheses (H_x) are defined sequentially in this order:

H_2 :

- The geometric mean ratio (THS Blade device/CIG) of S-PMA at Day 5 is less than 1
and
- The geometric mean ratio (THS Blade device/CIG) of 2-HEMA at Day 5 is less than 1
and

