9.6.3.1 Key Secondary Objectives

The key secondary objectives are to demonstrate the reduction of additional BoExp to selected HPHC given in [Table 2](#) in smokers who switch from CIGs to THS use compared to those who continue to smoke CIG. The statistical analysis for each of these additional BoExp for each THS arm (THS Blade device, THS Induction Mono device or THS Induction Mid device) will be done similarly to those belonging to the primary objective (except the Success Criteria). More specifically, the analyses described as primary estimand (see section [9.6.1.2](#)) can be repeated, replacing the endpoints listed in [Table 1](#) by those of [Table 2](#) and performing the analysis by THS arm sequentially.

The evaluation of the key secondary objectives will be done using a procedure of fixed sequence testing (see [Figure 2](#)). This first key secondary objective related to the THS Blade device will only be tested if the primary objective is demonstrated for all THS arms. This fixed sequence of study hypotheses ensures that the overall study-wise risk of type I error is preserved at the 2.5%.

If both the primary and first key secondary objectives are declared successful, then the 2nd key secondary objective will be tested with type I error level of 2.5%, this time using the contrast THS Induction Mono device vs. CIG and the BoExp listed in [Table 2](#). If this 2nd key secondary objective is also declared successful, then the 3rd key secondary objective can be tested similarly for the THS Induction Mid device arm. If, along the procedure from the primary objective up to the 3rd key secondary objective, any of the objectives are not declared successful, the sequence testing will stop, and further testing will not be permitted.

Figure 2. Representation of the Procedure of Fixed Sequence Testing

Confidentiality Statement

Data and information contained in this document are considered to constitute trade secrets and confidential commercial information, and the legal protections provided to such trade secrets and confidential information are hereby claimed under the provisions of applicable law. No part of this document may be publicly disclosed without the written consent of Philip Morris Products S.A.

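### The plan states two incompatible rules for primary success; if the joint contrast decides, the trial can succeed with one ineffective device

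*SAP*

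**What the plan says.** **Joint rule.** SAP 9.6.1.2 defines one estimate statement per biomarker, which "will allow contrasting all THS arms jointly against the CIG arm and will be used to assess the primary study hypothesis". SAP 9.6.1.3 adds: "While only the contrast between the three THS arms jointly and CIG at Day 5 will be used for the primary objective assessment". Protocol 12.5.1.4 and 12.5.1.6 carry the same text. Both documents then list the joint comparison as one item and the three device-versus-CIG comparisons as three further items. The SAP also plans one-sided 2.5% device contrasts, but gives them another role: "These contrasts will be used to assess the key secondary objectives 1, 2 and 3".

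**Every-device rule.** SAP 3.5.1 opens with "The primary study hypothesis is that there is a reduction of each and every of the BoExp to the selected HPHC" and lists 15 conditions (three devices by five biomarkers), all joined by a logical and. Protocol 12.9.3 says "every BoExp for each THS arms need to pass for the objective to be considered demonstrated". The statistical analysis paragraph of the protocol synopsis plans a one-sided pairwise test for each THS version. Under SAP 9.6.3.1, the first key secondary objective "will only be tested if the primary objective is demonstrated for all THS arms". SAP section 6 cubes the per-arm power to cover three arms.

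**Success sentence.** SAP 9.6.1.2 and Protocol 12.5.1.5 begin "The study will be declared successful if all ratios of the geometric means between every THS arms" and go on to require ratios below 1 for all five biomarkers. SAP 3.5.2 requires a reduction on each of the five endpoints and does not mention devices.

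SAP section 7 (changes from the protocol) does not address the matter. The contrast coefficients are left to be set when the class variables are coded.

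**The concern.** A programmer who follows SAP 9.6.1.3 would code one averaged contrast per biomarker, five tests in all. One who follows SAP 3.5.1 would code fifteen. An average over three devices can lie well below 1 when one of them does nothing, so the two analyses can give opposite verdicts on the same data.

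The claim in the primary hypothesis is that Blade, Mono and Mid each reduce exposure. Requiring all 15 tests is an intersection-union test and holds that claim at one-sided 2.5%. The joint contrast tests a different hypothesis and does not control the error rate of the three-device claim. It would also open the key secondary sequence without every device having been demonstrated. SAP Table 5 ends the blinding of statisticians when the SAP is finalized, so a rule settled afterwards, at coding, could be chosen with the data in view.

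**Working it through.** **1. Inputs.** GMR and GCV come from SAP Table 7 (four prior studies, five biomarkers). There are 20 subjects per arm, and 15% loss leaves n = 20 × 0.85 = 17. Tests are one-sided at 2.5%. The SD on the log scale is s = √ln(1 + GCV²).

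**2. The plan's own power.** For a two-sample t-test, SE = s√(2/n) and df = 2n − 2. The least favourable case is 3-HPMA in study 1970982:

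- s = √ln(1 + 0.3957²) = 0.3814
- ln 0.5286 = −0.6375
- SE = 0.3814 × √(2/17) = 0.1308
- noncentrality = −4.87, power = 0.9971

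The five biomarkers multiply to 0.9957 for one arm, and 0.9957³ = 0.987 for three. The other three studies exceed 99.9%. This agrees with the SAP's figures of above 99% per arm and at least 0.99³ = 97% overall. That calculation assumes the every-device rule.

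**3. Joint contrast with one ineffective device.** Assumptions: weights of 1/3 each, a Day 5 approximation to the mixed model, and independent biomarkers. One device has GMR 1 on all five biomarkers; the other two have the Table 7 GMR.

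- δ = (2/3) ln GMR
- SE = s√(1/(3n) + 1/n)
- df = 4n − 4

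For 3-HPMA in study 1970982:

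- δ = (2/3)(−0.6375) = −0.425, an apparent ratio of 0.654
- SE = 0.3814 × √(1/51 + 1/17) = 0.1068
- noncentrality = −3.98, critical value −1.998, power = 0.9749

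Total NNAL gives 0.9838, MHBMA 0.9999, and 2-CyEMA and COHb 1.0000. The product is 0.959.

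Probability of declaring success, ineffective device included:

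| Input set | n = 17, third device GMR 1 | n = 17, third device GMR 1.25 | n = 20, third device GMR 1 |
|---|---|---|---|
| 1970995 (JP) | 99.9% | 98.7% | >99.9% |
| 1989156 (US) | 99.8% | 98.3% | >99.9% |
| 1959932 (EU) | >99.9% | >99.9% | >99.9% |
| 1970982 (JP) | 95.9% | 83.8% | 98.3% |

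Simulation with a shared CIG arm gives the same picture; its lowest value is 95.8%.

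**4. Sensitivity, lowest input set (1970982), n = 17.**

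- Weight on the ineffective device of 0.25, 0.33, 0.40 or 0.50: 98.8%, 95.9%, 90.0% or 70.0%.
- Biomarker correlation of 0.5 or 0.9: 96.1% or 97.2%.

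**5. Every-device rule on the same cases.** With one device ineffective on a single biomarker, the 15-test rule passes in 2.4–2.6% of simulated trials (nominal bound 2.5%), against 97.5–100% under the joint contrast. With the device ineffective on all five, the 15-test rule passes in under 0.1%. When all three devices work as planned, simulated power with the shared CIG arm is 98.7% or more at 17 per arm and at least 99.7% at 20.

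**The case against.** The strongest reply is that most passages defining success already state the every-device rule: Protocol 12.9.3, the 15 conditions in SAP 3.5.1, the gate, and the plural ratios in the success sentence. Both documents call the three-part primary objective a joint evaluation, so the word could mean that all three must hold. If the estimate statement were coded as three rows, each tested, it would equal the every-device rule.

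That is the more natural reading of the success sentence, but it does not remove the conflict. The joint comparison is listed apart from the three device comparisons, so it is a separate quantity. The device contrasts are assigned to the key secondary objectives. The phrase covering every THS arm in the success sentence is also the label of the single contrast. Nothing in the text calls for three rows.

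Three further points stand and limit the finding:

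- An ineffective device is far from the planning ratios of 0.08 to 0.53, and under those ratios the two rules nearly always agree.
- A false key secondary claim stays at or below 2.5%, because each device is tested again in sequence. That protection does not reach the primary claim.
- The device-level results are reported, so an ineffective device would be visible even if the formal verdict were success.

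Finally, the protocol reviewed is version 2.0, while the SAP revision aligns to version 3.0. The stated purpose of that amendment is the timing of the COHb sample, so the text at issue has probably not changed, but this should be confirmed.

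**Conclusion.** The contradiction is real and must be resolved before analysis. If the joint contrast decides, success is declared in 95.9% to nearly 100% of trials with one wholly ineffective device, against at most 2.5% under the 15-test rule. These percentages rest on a single averaged contrast with equal weights, 17 evaluable subjects per arm, Table 7 inputs and independent biomarkers. The conclusion survives other weights (70.0% at the lowest, with half the weight on the ineffective device) and correlated biomarkers. They show what the joint rule permits and do not forecast the result.

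**What to change.** In SAP 9.6.1.2 and Protocol 12.5.1.4–12.5.1.5, write out three Day 5 contrasts with coefficients for each of the five biomarkers: Blade minus CIG, Mono minus CIG, Mid minus CIG. State that the primary objective is met only if all 15 one-sided 2.5% tests are significant, that is, all 15 upper 97.5% bounds of the geometric mean ratio lie below 1. Note that this is an intersection-union test and needs no alpha adjustment. In SAP 9.6.1.3 and Protocol 12.5.1.6, make the joint contrast supplementary and give its weights.

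The cost is wording in both documents, plus submission of the protocol amendment to the ethics committee under Protocol 1.1. The one-sided device contrasts are already planned, no subjects or data are added, and power for all 15 tests stays above the stated 97%.

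A separate wording correction can be made at the same time. SAP 9.1.7 should say that testing continues only if the preceding objective is demonstrated, and should drop its reference to a fourth key secondary objective, since only three exist.
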